1 SUMMARY

1.1 Title

Multicenter, Controlled and Randomized Trial to Evaluate the Combined Use of a Medical Device and a Food Supplement in the Control of Urinary pH of Patients with an Implanted Double J Stent.

1.2 Protocol code

Promoter Code: DEV-LCD-02-17

1.8 Ethical Research Committees (CEI)

All study materials have been reviewed and approved by:

- CEIC of the Hospital Universitari de Bellvitge (CEIm)

1.9 Description of the intervention between the arms of the trial (experimental and control):

EXPERIMENTALARM

• Food supplement study (II): Lit-Control® pH Down

- o Pharmaceutical form: capsules
- o Route of administration: oral
- o Dosage: 3 capsules / day.

• Study medical product: Lit-Control® pH Meter

- o Classification: in vitro diagnostic medical device.
- o Use: assessment of urinary pH.
- o Valuation method: by field effect transistors.
- o Periodicity of use: 1 time a day in the morning (first urine).

CONTROLARM

• Placebo:

- o Pharmaceutical form: capsules
- o Route of administration: oral
- o Dosage: 3 capsules / day.

• Study medical product: Lit-Control® pH Meter

- o Classification: in vitro diagnostic medical device.
- o Use: assessment of urinary pH.
- o Valuation method: by field effect transistors.

- o Periodicity of use: 1 time a day in the morning (first urine).

1.10 Phase of the clinical trial

Post-marketing.

1.11 Objective

Principal:

- To evaluate the efficacy of the food supplement Lit-control®pH Down in the prevention of double J stent calcification.

Secondary:

- Evaluate the efficiency of the Lit-control®pH Meter device and the Lit-control®pH Down food supplement in the pH control.
- Determine the safety of the food supplement Lit-control®pH Down.
- Evaluate compliance / adherence with the measures for the determination and control of pH recommended by the doctor.
- Know the cost-effective profile of the intervention (from the moment of placing the double J stent to its withdrawal).

1.12. Study design

Multicenter, prospective, randomized, double-blind, placebo-controlled study.

1.13. Disease under study

Process of calcification of the double permanent stent J.

1.14. Type of study

Clinical trial with sanitary product.

1.15 Study population

Adults who come to the urology / nephrology clinic who have recently had a double J stent or who have scheduled their placement and who are able to take charge of the urinary pH control at home.

1.16. Monitoring

Clever Instruments S.L. will be responsible for the logistics and monitoring of the study. A monitoring visit is planned to start and close the study by center. Real-time remote monitoring of the data record will be done throughout the study.

1.17. Treatment duration

Health product under study: 2 months (1 use / measurement per day).

Food supplement object of study: 2 months (3 capsules per day).

Placebo: 2 months (3 capsules per day).

2. INTRODUCTION AND JUSTIFICATION OF THE STUDY

Since the introduction of double ureteral stent J by Finney in 1978, its use has taken an important position in the management of obstructive uropathy (urolithiasis, stenosis and ureteral injuries, retroperitoneal fibrosis), in the postoperative period of ureteropyelic stenosis and transplantation renal.² The most severe complication associated with the use of the double J stent is calcification and the potential impossibility of removing the ureteral stent.^{3,4} The incrustation process that results in the calcification (partial or total) of the stent was described in 1995 by Getliffe as the "embedding cycle" .^{5,6} This cycle begins with colonization of the stent or urinary tract infection (UTI) by urea-releasing microorganisms, which contribute to an alkalinization of urine and a decrease in solubility of minerals in urine, facilitating the possibility of incrustation and subsequent calcification.⁵ This process occurs faster in some patients than in others, suggesting that there are patients more likely to have this complication.⁷

Several studies have shown the importance of urinary pH control (pH_v) to determine the frequency of stent incrustation, ⁸⁻¹⁰ this measure being a variable to be taken into account in the management of patients with indwelling stent. However, the level of pH_v is influenced by multiple factors, so its routine control is difficult to interpret.¹¹ Choong et al. (1999) described the nucleation pH (pH_n): the pH where the scale starts to form.¹² In his study he observed that the pH of the patients who developed a stent blockage and those who were not very similar (7.46 and 7.38 respectively), but observed that the pH_v of the patients who did not have incrustations was much lower and therefore had a much wider safety margin.¹²

As already mentioned, pH_v is influenced by various factors, but it is especially sensitive to diet.¹⁰ For this reason, hygienodietetic interventions (exercise, diet, fluid intake, etc.) are one of the preventive measures of incrustation of the stent of great utility, although its effectiveness is subject to patient adherence.

Lit-control® pH Down is a dietary supplement with an acidifying effect on urine, which helps to prevent complications arising from the alkalinization of urine. It contains L-methionine, phytin (calcium-magnesium phytate salt), zinc and vitamin A. The two active components in acidification of pH_v are L-methionine and fintine, while zinc and vitamin A increase the action of the phytin. Specifically, zinc favors the affinity of its affinity for calcium phosphate and vitamin A prevents its degradation by alkaline phosphatase.

L-methionine is an essential amino acid that plays an important role in metabolic processes. It is normally acquired through food and absorbed in the small intestine to be metabolized in the liver via cysteine to sulphate and protons (ANNEX 8). Consequently, its administration produces a significant reduction of urinary pH.

According to the European Association of Urology (UAE), urinary acidification with L-methionine up to pH 5.8 - 6.2 is recommended as a therapeutic measure for calcifications of struvite, calcium phosphate and ammonium urate at doses of 600- 1500 mg / day¹³. This recommendation is based on the results observed in Jarrar et al 1996¹⁴, where an acidification of the pH of the urine of the patients was observed from 7.5 to 5.5 after the administration of 1500-3000 mg / day (3-6 capsules). of 500mg / day). Also in the study of Hesse 1999 a significant reduction in urinary pH was observed up to pH = 6.0 after the administration of a single dose of 1500 mg of L-methionine, maintaining this effect for 24h¹⁵. In addition, a significant reduction was observed versus the control group in terms of the relative supersaturation for estuvite and

brushite in the urine of 24h15. In another more recent study, Siener et al. studied the circadian course of urinary pH after the administration of 1500 mg of L-methionine. They observed a strong decrease in urinary pH up to 2h after the administration of the amino acid that remained at significantly low levels for 8h, resulting in a pH level for 24h between 5.98 and 6.3216. Therefore, in order to guarantee therapeutic doses of L-Methionine (1500mg / day), the Lit-control®pH Down regimen to follow would be equivalent to 3 capsules per day (500 mg / capsule).

On the other hand, the device Lit-control® pH Meter is a medical device that allows patients to self-monitor their pHv daily in their own home, allowing a thorough control of the pH and the level of encrustation risk. The device has been validated for use in lithiasic patients17, with applicability in the treatment of other urological pathologies related to the acid-base balance of urine, calcifications of urinary stents, cystitis, urinary tract infections, painful bladder syndrome and bladder hyperactive

The aim of this study is to evaluate the efficacy of the food supplement Lit-control®pH Down in the prevention of the double J stent incrustation and in the urinary pH control together with the use of the Lit-control® pH Meter device.

3. OBJECTIVES OF THE STUDY

3.1 Main objective

- To evaluate the efficacy of the Lit-control®pH Down food supplement in the prevention of double J stent calcification.

3.2 Secondary objectives

- Evaluate the efficiency of the Lit-control® pH Meter device and the Lit-control®pH Down food supplement in the pH control.
- Determine the safety of the food supplement Lit-control®pH Down.
- Evaluate compliance / adherence with the measures for the determination and control of pH recommended by the doctor.
- Know the cost-effective profile of the intervention (from the moment of placing the double J stent to its withdrawal).

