6.2.1 Inclusion criteria

- Age ≥18 years.
- Patients who have recently had a double J stent (time less than a week) or who have scheduled their placement and are recommended to control the pH to avoid scaling / calcification.
- Patients who agree to participate in the study and provide their informed consent.

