6.3.2 Follow-up period

The follow-up will be 3 weeks up to a maximum of approximately 2 months, depending on the time from the inclusion visit (V0) to the extraction of the stent (Vf). During this period, the patient will self-monitor their urinary pH level at home and register the respective data with the domiciliary CRD. The patient will be offered the possibility of registering the home self-management data directly to an online CRD through a personalized link that the researcher will provide during the inclusion visit and that will be generated through a computer program. If you only register it on paper, you must deliver it to the researcher at the next visit.

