6.3.3 Baseline Visit - V0 (inclusion)

The researcher will consecutively include the patients as they come to their consultation. The investigator will inform the patient about the study and will provide the information sheet. In case the patient agrees to participate in the study, they must sign the informed Consent Form that the researcher will also provide. Subsequently, the researcher will ensure that the patient meets all the inclusion / exclusion criteria and proceed to confirm their inclusion in the study. If the patient is eligible but does not give informed consent and / or does not meet any of the inclusion / exclusion criteria, then the investigator will add a new case to the list of eligible patients without recording any other information related to the patient.

Sociodemographic data and medical and family history of interest will be recorded, as well as the date and reason for stent placement. The data will be recorded necessary to classify patients according to the "Blockage risk factor" 23. In addition, a urine test of 2 hours fasting will be requested.

At the end of the visit, the patient will be given the treatment assigned by randomization and the link to the electronic domicile CRD and on paper. The patient will be reminded that at the next visit they should return (empty or not) the blisters of the treatment administered.

NOTE: For reasons derived from the logistics and the tests to be performed with the stent, researchers should try to enter the data in the online CRD in real time (or within a 24 hour timeframe) both at the time of placement of the stent as of extraction. This will allow a follow-

up and an appropriate time of logistical management that guarantees that the stents arrive in optimal conditions for their study to the specialized center of Palma de Mallorca.

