6.3.4 Visit Final Control - Vf (stent removal)

The time of the final visit will not be determined by protocol but according to the moment in which, by usual clinical practice, the double j stent is extracted in a programmed manner (which should be between 3 and 8 weeks after the baseline visit). During this visit, the data regarding the symptoms perceived by the patient during the time with the stent will be recorded, data relative to the received treatment (adherence, presence of adverse effects, date of beginning and end of the pH control, complications derived from the stent and data on stent removal (date, complications, presence / degree of calcification, etc.) and this will be sent (after conditioning) * to be analyzed by an expert to determine the presence of any of the different stages of calcification (presence of bacterial biofilm, incrustations and / or calcifications.) During this visit, the patient will deliver his / her home diary with the pH control data and annotated supplement record (as long as it has not already been registered directly with the home eCRD) and will also transfer the product excess (food supplement blisters) and, if possible, also empty blisters.

On the other hand, pharmacoeconomic data will also be recorded in order to determine the cost-effective profile of the intervention.

* The conditioning of the stent for storage and subsequent delivery to the specialist who is going to carry out his study is described in the Investigator's Manual.

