7.2 Secondary valuation variables

- Sociodemographic and anthropometric variables (sex, age, weight, height, BMI, marital status, work situation, toxic habits).
- Family history of obstructive uropathies.
- Personal clinical history of interest (previous nephritic colic, kidney transplant, acute pathology of interest, chronic pathology (HBP, Chronic Kidney Disease, Diabetes and others).

- Anatomical alterations in the urinary system.
- Previous incidence of obstructive uropathy (urolithiasis, stenosis and ureteral injuries, retroperitoneal fibrosis).
- Previous need for stent (indwelling stent reason, date of stent placement and removal, type of stent and symptoms (if any) associated with it)
- Date of placement and removal of the double J stent (current) and Total time with double J stent until its withdrawal (days).
- Total pH control time (days).
- Urine analysis of 2 hours in basal fasting (volume of urine, pH, creatinine, uric acid).
- Urine culture (infection: yes / no).
- Complications observed due to placement or permanence of the stent and symptoms associated with indwelling stent.
- Image of the stent (scanner or X-ray).
- Adherence to treatment / recommendations of the doctor.
- Adverse events attributable to the treatment or study recommendations.
- Data on stent removal (date, complications, type of procedure and duration of extraction).
- Satisfaction of the researcher with preventive therapy.
- Patient satisfaction with preventive therapy.
- Pharmacoconomic data (direct costs): stent placement intervention, consultation visits, emergency visits, hospitalizations, medication administered, intervention (cost and type) for stent removal and total direct cost of the patient during the study (estimated at from the data provided by the center).

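### The cost and stent-symptom windows start at stent placement instead of randomisation, so pre-treatment costs and events enter the arm comparison for patients already stented at inclusion

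*Protocol*

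**What the plan says.** **Cost window.** The secondary objective in 3.2, repeated in 1.11, is "Know the cost-effective profile of the intervention (from the moment of placing the double J stent to its withdrawal". Section 7.2 lists the direct costs, beginning with "stent placement intervention, consultation visits, emergency visits, hospitalizations", and ends with a differently worded total: "total direct cost of the patient during the study". Section 7.4 makes cost-effectiveness, based on the observed direct costs, an end point.

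**Timing of inclusion.** Section 6.2.1 admits "Patients who have recently had a double J stent (time less than a week) or who have scheduled their placement". Section 6.3.3 says of V0: "At the end of the visit, the patient will be given the treatment assigned by randomization". Section 6.3.2 sets the length of follow-up "depending on the time from the inclusion visit (V0) to the extraction of the stent (Vf"; section 6.3.4 expects this to be 3 to 8 weeks.

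**Symptoms and complications.** At the final visit (6.3.4), "the data regarding the symptoms perceived by the patient during the time with the stent will be recorded". The variable list in 7.2 includes complications arising from inserting the stent as well as from its remaining in place. Section 8.2 prescribes chi-square or Fisher tests for the qualitative variables in the data collection notebook.

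**Adverse events.** Section 11 defines these as occurring after randomisation.

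**The concern.** A comparison of randomised arms should count what happens from randomisation onwards. Here the time origin is stent placement, which can lie on either side of randomisation.

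- **Stented before V0.** The placement procedure, and any stay or emergency visit before V0, cannot be an effect of the supplement but is part of the total cost compared. Symptoms and placement complications that arose before the first capsule are likewise recorded as outcomes.
- **Stented after V0.** The cost window opens only at placement, so any resource use between V0 and placement falls outside it.

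The protocol is also inconsistent: the objective, the cost total in 7.2 and the follow-up definition describe different windows, and section 11 uses yet another origin for adverse events. At stake are the precision of the incremental cost and the sensitivity of the symptom and complication comparisons.

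**Working it through.** **1. The plan's own figure.** The protocol gives no figure for these windows. Its only computed figure is the sample size in 6.8. With effect size 0.6, 80% power and two-sided 5% (the level is assumed, since 6.8 does not state it), the normal formula gives 44 per arm. Dividing by the Mann-Whitney efficiency 3/π gives 46.1, so 47 per arm and 94 in total; 94/0.9 = 104.4, so 105. Both figures reproduce, and this point does not alter them. The 47 per arm is used below.

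**2. The windows side by side.**

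| Item | Starts | Section |
|---|---|---|
| Cost objective | stent placement | 1.11, 3.2 |
| Cost total | start of study, not defined further | 7.2 |
| Follow-up | V0 | 6.3.2 |
| Stent symptoms | stent placement | 6.3.4 |
| Stent complications | placement complications included | 7.2 |
| Adverse events | randomisation | 11 |

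**3. Share of time affected.** Take V0 to Vf as 21 to 56 days (6.3.4).

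- Stent placed 6 days before V0: pre-treatment share of the stent-in-place period = 6/(6+21) = 22.2%, down to 6/(6+56) = 9.7%.
- Stent placed 7 days after V0 (assumed; the protocol sets no limit): share of V0 to Vf outside the cost window = 7/21 = 33.3%, down to 7/56 = 12.5%.

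These two shares concern different patients. The protocol does not give the mix, so they cannot be added.

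**4. Effect on the cost comparison.** Let k be the SD of pre-V0 cost across the patients of an arm, divided by the SD of later cost, with the two independent. The standard error of the difference is multiplied by √(1+k²). For illustration, take a true difference of 0.6 SD of later cost and 47 per arm.

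| k (assumed) | √(1+k²) | SE increase | Power |
|---|---|---|---|
| 0 | 1.00 | none | 0.83 |
| 0.25 | 1.03 | 3% | 0.81 |
| 0.5 | 1.12 | 12% | 0.74 |
| 1 | 1.41 | 41% | 0.54 |

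Nothing in the protocol says which k applies.

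**5. Dilution of symptoms or complications.** This step supposes an ever/never item. If a share q of both arms already had the event before V0, independently of later events, the recorded rate is 1−(1−q)(1−p), so the arm difference shrinks by the factor (1−q). With assumed post-V0 rates of 40% v 15% (25 points, power 0.78 at 47 per arm):

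- q = 10%: 22.5 points, power 0.63
- q = 20%: 20.0 points, power 0.50
- q = 30%: 17.5 points, power 0.40

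These rates illustrate the mechanism and are not estimates for this trial.

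**The case against.** **Costing the whole stent episode is a recognised choice, and the protocol states it openly.** This stands as a reason to keep the episode cost as a descriptive figure. It does not make pre-randomisation cost informative about the supplement, nor does it reconcile 3.2 with the total in 7.2.

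**No bias.** A reader might infer that the cost difference is biased. It is not: pre-V0 costs and events are balanced in expectation, so they add noise and dilution only.

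**The noise may be small.** Section 7.2 says total cost is estimated from data supplied by the centre, and codes are allocated by centre (6.5). If placement is costed at a centre rate, it varies little within a centre and largely cancels between arms. Later cost also includes removal and hospitalisations. A low k is therefore plausible, and values well above 1 would need support that the protocol does not give.

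**Symptoms need not be one yes/no item.** A reader might infer that the answer is already settled before treatment starts. No section codes symptoms that way, and the notebook is not shown. Placement complications appear in the variable list of 7.2; the final-visit text in 6.3.4 speaks only of complications from the stent. Neither stent symptoms nor placement complications are among the end points in 7.4, though the general tests in 8.2 reach them.

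**Lost days on product are an inference.** The protocol does not say on which day a patient awaiting placement starts the capsules. Products are supplied free (Annex 4), and no specific resource use between V0 and placement is identified. What stands is only that, if such use occurs, the window excludes it.

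**Starting at V0 could create its own asymmetry.** A placement admission would be excluded for a patient stented just before V0 but included for one stented just after. This is correct, and the fix must deal with it.

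**Conclusion.** The point holds in a limited form. The protocol fixes a cost origin that is not randomisation, states a second, different window in 7.2, and records stent symptoms over a period that can begin before treatment. For patients already stented at V0, pre-treatment costs and events enter the arm comparison; for those stented later, any resource use between V0 and placement is left out.

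The consequence is added variance and dilution in secondary variables that the trial is not powered for. The primary encrustation score, the sample size of 94 (105 with losses), adverse events and extraction outcomes are unaffected.

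The size cannot be fixed from the protocol, which gives neither cost SDs, nor symptom rates, nor the mix of patients stented before and after V0. A rise in the standard error of the cost difference of about 3% to 41% corresponds to the assumed SD ratios of 0.25 to 1 and rests on independence of earlier and later cost. The power figures in the working should not be read as predictions.

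**What to change.** - **One comparison window.** Reword 1.11, 3.2 and 7.2 so that the incremental cost comparison runs from randomisation (V0) to Vf for every patient.
- **Placement costs apart.** For every patient, whether stented before or after V0, leave the placement procedure and its associated admission out of that comparison and report them separately as descriptive data. Applying this to all patients avoids costing those stented just before and just after V0 differently.
- **Onset field.** At Vf, record whether each stent symptom or complication began or worsened after V0. Compare the arms on those, and list earlier ones as baseline. This matches the treatment of adverse events in section 11.

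**Cost.** Wording in three sections and one extra field in the notebook, with no added visits or patients. The field should be in place before data collection, because onset relative to V0 is hard to recover afterwards. The downside is that the headline cost no longer covers the whole stent episode, though this can still be reported descriptively.
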